A population pharmacokinetic (PK) analysis planned in the whole subject population, will obtain sparse blood samples to determine plasma concentrations of LF111 at Visits 2 and 4. In total, four blood samples will be collected: two samples each will be collected during the 1st cycle (Visit 2: Cycle 1, Week 3, Day 20±2) and during the 6th cycle (Visit 4: Cycle 6, Week 3, Day 20±2) of treatment.

Number of subjects (planned):

Screened (enrolled): Approximately 1500. Screening will continue until a sufficient number of subjects have been allocated to treatment.

Allocated to treatment: At least 995 non-breastfeeding subjects, including a minimum of 75 subjects > 35 years.

Note: Breastfeeding women are also allowed to be enrolled in the trial.

Collected medication cycles: At least 5000 evaluable cycles (cycles with intercourse without back-up contraceptive at least once per month based on electronic diary question 'Did you have sexual intercourse since the beginning of the cycle?') for non-breastfeeding subjects aged ≤ 35 years (at the time of trial enrollment).

At least 200 women having completed 13 cycles of treatment will be analyzed for safety.

Diagnosis and main criteria for inclusion:

1. Sexually active, postmenarcheal and premenopausal female subjects at risk of pregnancy including breastfeeding women with no upper age limit.
2. Female subjects at risk of pregnancy, between the ages of 15 and 17 (inclusive) provided that
 - Applicable national, state and local laws allow subjects in this age group to consent/assent to receive contraceptive services, and
 - All applicable laws and regulations regarding the informed consent/assent of the subjects to participate in clinical trials are observed.
3. Regular cycles during the last six months before consent/assent when not using hormonal contraception.
4. At least three complete menstrual cycles after delivery (only applicable for women who were pregnant within the last six months and for non-breastfeeding women).
Breastfeeding women can be included six weeks after delivery irrespective of menstrual cycles post-delivery.
5. At screening, maximum systolic blood pressure (median value of three values) ≤ 159 mm Hg and diastolic blood pressure (median value of three values) ≤ 99 mm Hg.
6. Be able and willing to provide written informed consent or assent if the subject is adolescent, prior to undergoing any trial-related procedure.
7. Willing to use trial contraception for thirteen 28-day cycles.

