Duration of treatment for the individual subject: 13 sequential cycles of 28 days

Test product, dose and mode of administration:

LF111 coated tablets (4.0 mg drospirenone), oral administration

Reference therapy, dose and mode of administration: Not applicable.

Criteria for evaluation:

Efficacy:

Primary:

- Pearl index (PI) from evaluable cycles in non-breastfeeding women aged ≤ 35 years (at the time of trial enrollment)

Secondary:

- Pearl Index based on overall cycles (overall PI) in women aged ≤ 35 years (at the time of trial enrollment)
- PI for method failures in women aged ≤ 35 years (at the time of trial enrollment)
- Pregnancy ratio in women aged ≤ 35 years (at the time of trial enrollment)
- Overall PI, PI for method failures, PI (using evaluable cycles) and pregnancy ratio (life table analysis) in all women
- Overall PI, PI for method failures, PI (using evaluable cycles) and pregnancy ratio (life table analysis) in women aged > 35 years

Data from breastfeeding women will be excluded from the efficacy analyses but included in the analyses regarding safety and tolerability.

Safety/Tolerability:

- Adverse events (AEs)

- Vital signs
- Clinical laboratory parameters
- Vaginal bleeding pattern
- IMP acceptability

Pharmacokinetics:

- DRSP plasma concentrations
- Area under the curve (AUC)
- Volume of distribution
- Apparent clearance

Statistical methods:**Statistical analysis:**

Analysis of the primary efficacy variable defined as PI based on evaluable cycles in non-breastfeeding women aged ≤ 35 years (at the time of trial enrollment) will be performed for the Full Analysis Set (FAS). Two-sided 95% confidence interval (CI) for the PI will be calculated assuming that events of pregnancy have a Poisson distribution.

Secondary efficacy analysis will be based on the FAS. Two-sided 95% CIs will be calculated for the overall PI and the method failures PI.

Life table analysis: The pregnancy rate at each cycle and the cumulative pregnancy rate will be calculated (95% CI).

Analysis of safety endpoints will be conducted using the Safety Set only.

All adverse events (AEs) and treatment-emergent AEs (TEAEs) will be summarized by calculating the number and percent of subjects with AEs by preferred term and system organ class. Also TEAEs will be summarized by severity and relationship to treatment. Number and percent of TEAEs leading to trial termination will be provided.

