6 Urinalysis: leukocytes, nitrite, protein, glucose, ketones, blood, pH, urobilinogen, bilirubin, hemoglobin – dipstick.

7 V1a: Height has to be determined for all subjects. V1b to V6: Height has only to be determined in adolescent subjects (i.e. < 18 years of age).

8 In addition, each subject will perform a urine dipstick pregnancy test at home at the beginning of each new medication cycle. In case of an equivocal or positive urine pregnancy test, a quantitative serum pregnancy test has to be performed for confirmation.

9 On Day 10 + 2 days of each cycle, the subjects will be called by the site staff to collect information on adverse events which might have occurred, and to confirm e-diary compliance. Throughout each cycle, subjects will be called by site staff to review e-diary compliance as needed.

10 Only electrolytes.

11 Measurements of vital signs will be repeated twice with a break of one minute between them at each visit in sitting position, after at least five minutes of rest. The subject should not talk.

12 Two blood samples per visit will be collected to determine plasma concentrations of LF111 at Visits 2 and 4 and should ideally be one hour apart (between 45 and 120 minutes after the first sample) without a LF111 administration in between.

13 The subject will be asked if she has a wish of pregnancy at each visit. In case of a positive answer, the subject will be discontinued.

14 Once the e-diary has been assigned to a subject, a practice diary (training section in e-diary) has to be actively completed.

15 The investigator should arrange for the subject's further contraceptive treatment or make an appropriate referral, as needed, at V5. Consecutive contraceptives should be started after last IMP intake and should be used at least until V7/Follow-up. This arrangement is outside the trial and costs will not be covered by the Sponsor.

16 The subject will be asked by the investigator: Are you satisfied with this method? Answer options: strongly agree, agree, undecided, disagree, strongly disagree, no answer. Furthermore, for women who switched from another oral contraceptive method to the IMP will be asked by the investigator: How was your wellbeing during the intake of the IMP in comparison to the time when you took your former oral contraceptive? Answer options: better, unchanged, worse, no answer.

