2.2.2 Secondary Efficacy Endpoints

Cycles of breastfeeding women will be excluded from the efficacy analyses but included in the analyses regarding safety and tolerability.

Secondary efficacy endpoints are:

- Pearl Index based on overall cycles (overall PI) in women aged ≤ 35 years
PI based on overall cycles will include all pregnancies which will occur during the trial in women aged ≤ 35 years (at the time of trial enrollment).
- PI for method failures in women aged ≤ 35 years
Method failures PI will include all pregnancies of women who used the IMP correctly. Pregnancies are to be excluded from the calculation if in medication cycles of conception or in the previous medication cycles depending on the date of conception:
 - not all active tablets are taken (based on returned medication, recordings in the e-diary and non-compliance based on DRSP levels, if necessary)

- there is a tablet free interval between the previous medication cycle and the medication cycle of conception
- vomiting or diarrhea is documented
- administration of prohibited prior or concomitant therapy as detailed in Section 10.7 of the Clinical Trial Protocol is documented
- Pregnancy ratio in women aged ≤ 35 years (Life table analysis)

In addition to PI analysis, method failure life table analysis and life table analysis on evaluable cycles will be performed in women aged ≤ 35 years (at the time of trial enrollment) in order to have the pregnancy rate at each cycle and cumulative pregnancy rates for 6 and 13 cycles. For life table analysis on evaluable cycles, only medication cycles of non-breastfeeding women will be considered as evaluable as defined in 2.2.1 and will be included in analysis. If the cycle is not evaluable but the subject became pregnant in this cycle, the cycle has to be included in the analysis. All pregnancies following premature termination of IMP will not be included in calculations if they occur later than seven days after the last tablet intake (active or placebo). Method failure pregnancy rates similar to method failure PI will include only those cycles of women who use the IMP correctly and include only perfect medication cycles as described in Section 5.5 of non-breastfeeding women.

- Overall PI, PI for method failures, PI for evaluable cycles and pregnancy ratio (life table analysis) in all women

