Listing EX15	Subjects with Long-Term Treatment of Any Medication That Might Interfere with the Efficacy of Hormonal Contraceptives Prior to Visit 1b
Listing EX16	Subjects Who Received Human Chorionic Gonadotropin or Co-Medication Containing Human Chorionic Gonadotropin Within a Month Prior to V1b
Listing EX17	Subjects with Progestin-Releasing Intra-Uterine Device or Contraceptive Implant Received or in Place within the Last 2 Months Prior to Visit 1a
Listing EX18	Subjects with history of clinically significant psychiatric illness or suicide risk

Additional trial conduct criteria deviations will be classified as follows:

Number	Name
Listing DRM01	Subjects Who Became Pregnant During the Study
Listing DRM02	Cycles when Vomiting or Diarrhea is Documented
Listing DRM03	Cycles with Administration of Prohibited Concomitant Therapy
Listing DRM04	Subjects Who did not Meet Inclusion/Exclusion Criterions
Listing DRM05	Listing and Chart with Treatment Cycles
Listing DRM06	IMP Gaps of More Than 48 Hours
Listing DRM07	Adverse Events of Special Interest
Listing DRM08	Non-Complete or Non-Correct Treatment Diary Records
Listing DRM09	Specification of Subject Withdrawn During Treatment
Listing DRM10	Specification of Subject Withdrawn During Screening
Listing DRM11	Protocol Deviation from eCRF
Listing DRM12	Scenarios for first IMP intake preceding V1b
Listing DRM13	Subjects with Partial Date of Last IMP Intake in eCRF
Listing DRM14	Treatment Compliance According to Drug Accountability
Listing DRM15	Subjects for Whom IMP Was Dispensed but Have No eDiary Records
Listing DRM16	Subjects Who Have Cyst Larger Than 30 mm

All decisions made during DRM will be documented in the DRM report.

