Method failure pregnancy*	All on-drug pregnancies of women who used the IMP correctly. Pregnancies are to be excluded from the calculation if in medication cycles of conception or in the previous medication cycles depending on the date of conception: 
 - not all active tablets are taken (based on returned medication, recordings in the e-diary and non-compliance based on DRSP levels, if necessary) - there is an active tablet free interval between the previous medication cycle and the medication cycle of conception. Tablet free interval will be determined by record from treatment diary. - vomiting or diarrhea is documented - administration of prohibited prior or concomitant therapy as detailed in Section 10.7 of the Clinical Trial Protocol is documented
Exposure cycles	28-day cycles, where at least one treatment diary entry of IMP intake is available. In addition, a cycle will be an exposure cycle if the subject become pregnant during this cycle regardless this cycle was a 28-day cycle or not.
Evaluable cycle	Cycles are exposure cycles with intercourse without back-up contraceptive at least once per cycle based on electronic diary question 'Did you have sexual

	
intercourse since the beginning of the cycle?" and answered with: 'Yes I had sexual intercourse without additional contraception'.
 
Also, cycle is to be defined as evaluable if:
 
 - Subject became pregnant at the respective cycle regardless back-up contraception was used or not. - Cycle has missing answer about intercourse or answered "I had NO sexual intercourse at all" but subject became pregnant at the respective cycle. 
Cycle will not be defined as evaluable if subject did not become pregnant and:
 
 - The question was answered with 'Yes I had sexual intercourse with additional contraception'. - Cycles with NO intercourse. - Cycle has missing answer about intercourse.
Perfect cycle*	
Evaluable cycles which have no:
 
 - >48h tablet free interval during the second IMP intake till day 24 of each cycle or >144h interval between the last IMP intake and the first IMP intake in consecutive cycles. Tablet free interval calculation will not take into account cycle days 25-28. - 4 or more days with forgotten tablets intake during 1-24 cycle days. - Protocol deviations having effect on this cycle.

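### Drospirenone levels may exclude pregnancies from the method-failure Pearl Index, with no stated limit and no matching criterion for non-pregnant cycles

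*SAP*

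**What the plan says.** **Numerator.** SAP 2.2.2 and the definitions table in SAP 5.5 count as method failures the pregnancies of women who used the product correctly. One ground for exclusion, looking at the cycle of conception or the preceding cycle according to the conception date, is that "not all active tablets are taken (based on returned medication, recordings in the e-diary and non-compliance based on DRSP levels, if necessary". The other grounds are a tablet-free interval between cycles, vomiting or diarrhea, and prohibited medication. Neither section gives a concentration limit, a time-after-dose rule, a qualifying sample, a decision-maker, or the circumstances that make DRSP levels necessary.

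**Samples.** The protocol synopsis plans that "two samples each will be collected during the 1st cycle (Visit 2: Cycle 1, Week 3, Day 20±2) and during the 6th cycle". SAP section 1 agrees: "Two blood samples per visit will be collected to determine plasma concentrations of LF111 at Visits 2 and 4", ideally one hour apart. Treatment lasts "13 sequential cycles of 28 days". The synopsis gives population pharmacokinetics as the purpose, and SAP 2.2.5 leaves that analysis to a separate SAP.

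**Denominator.** The method-failure index is divided by perfect cycles (SAP 5.5). These are evaluable cycles without a long tablet-free interval, without four or more forgotten tablet days in Days 1 to 24, and without protocol deviations that affect the cycle. DRSP levels are not named there or in the compliance section (SAP 5.4.2). No title among the data review listings in SAP 3.3 names them either; the nearest is DRM14, "Treatment Compliance According to Drug Accountability". A note to the definitions table adds that when a pregnancy fails the method-failure definition, its own cycle is not perfect.

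**Timing.** SAP 3.3 assigns pregnancies to categories at a data review meeting held after database lock and before the final SAP.

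**The concern.** The method-failure index estimates how often the product fails when it is taken correctly. It stays interpretable only if correct use is judged by the same evidence in cycles with and without a pregnancy. Here one kind of evidence, "non-compliance based on DRSP levels, if necessary", is written into the rule for pregnancies and into no rule for other cycles. It is optional, it has no stated limit, and it is applied by people who know that the cycle ended in pregnancy. A pregnancy with full intake by both tablet count and diary could be excluded on a level, while a non-pregnant cycle with the same level would stay in the denominator. The result would make the product look better under correct use than the data support. Method failures are likely to be few, so a single such decision is visible in the estimate.

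**Working it through.** **1. The plan's own figure, used only for scale.** Inputs from SAP 2.6: 920 subjects, 24.8% back-up use or no intercourse, 45% drop-out; 13 cycles from the synopsis. If drop-outs contribute no cycles, 920 × 13 × (1 − 0.248) × (1 − 0.45) = 4,946.7, which is 1.1% below the stated 5,000 evaluable cycles. Perfect cycles are a subset of evaluable cycles. The documents do not give their number, so I assume 3,000 to 5,000.

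**2. Which conceptions a planned level can reach.**
- Cycles with a planned sample: 2/13 = 15.4%.
- The rule covers the cycle of conception or the one before it, so conceptions in cycles 1, 2, 6 and 7 are reachable: 4/13 = 30.8%.
- With 45% drop-out spread evenly, the share still treated in cycle i is 1 − 0.45 × (i − 1)/13, which sums to 10.3 over 13 cycles. Cycles 1, 2, 6 and 7 give 1.000 + 0.965 + 0.827 + 0.792 = 3.585, and 3.585/10.3 = 34.8% of exposure.
- Of an assumed 4 to 10 pregnancies spread evenly over cycles, 4/13 gives 1.2 to 3.1 with a planned level in reach.

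**3. What a level can show.** The criterion asks whether all 24 active tablets (SAP 2.5) were taken. The samples fall on one day between Day 18 and Day 22, so at least the active tablets of Days 23 and 24 always come later. Two samples about an hour apart cannot document intake on every earlier day either.

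**4. Effect of one exclusion.** The index is 1300 × x/n for x method failures in n perfect cycles. Excluding one pregnancy and its cycle gives 1300 × (x − 1)/(n − 1), a relative fall of almost exactly 1/x: 25% for x = 4 and 10% for x = 10.

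For an assumed x = 8, with exact Poisson 95% limits (lower 0.5χ²(0.025; 2x), upper 0.5χ²(0.975; 2x + 2)):

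| Perfect cycles | No DRSP exclusion | One DRSP exclusion |
|---|---|---|
| 5,000 | 2.08 (0.90 to 4.10) | 1.82 (0.73 to 3.75) |
| 3,000 | 3.47 (1.50 to 6.83) | 3.03 (1.22 to 6.25) |

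The upper-limit formula printed in SAP 5.5 differs from the one used here; that is a separate matter.

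**5. The part due to one-sidedness alone.** Suppose the same marker also removed 10% of non-pregnant perfect cycles within the four reachable cycles, with perfect cycles spread evenly. The denominator becomes 4,992 × (1 − 0.10 × 4/13) + 7 = 4,845.4, and the index is 1300 × 7/4,845.4 = 1.88, against 1.82 under the rule as written. The rest of the fall from 2.08 comes from excluding a pregnancy on a criterion without a stated limit. To offset one exclusion among 8 fully, 1/8 = 12.5% of all non-pregnant perfect cycles would have to go as well.

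**The case against.** Several points on the other side stand.

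- **Limited reach.** The endpoint is secondary, gets a descriptive interval, and carries no success limit. Sparse sampling also limits the harm: a level matters only for the few pregnancies within reach that tablet count, diary and the other criteria have not already excluded.
- **Visibility.** Table 15.1.7.1.1 (SAP 5.1.2) reports the deviations that lead to exclusion of pregnancies, and SAP 3.3 requires review decisions to be documented. This makes an exclusion traceable, but does not make the rule even-handed.
- **Value of the marker.** It is the only listed check on intake that does not depend on diary entries or returned tablets. That is a reason to keep it as a sensitivity analysis.

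Three stronger readings are tempting, and the documents do not support them.

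- A reader might infer that levels bear on only 2 of 13 conception cycles. The rule also looks at the preceding cycle, so cycles 2 and 7 are reachable.
- A reader might infer that a level can never touch a non-pregnant cycle, or that downward is the only possible direction. The perfect-cycle definition has an open ground for protocol deviations, which could admit a DRSP finding. What the text supports is that no DRSP criterion is named for those cycles.
- A reader might infer that no cut-off exists at all. Only the synopsis of the protocol is available, parts of the SAP are missing, and the pharmacokinetic SAP is separate. A limit, or sampling at suspected pregnancy, could be set there; if so, SAP 5.5 should cite it.

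**Conclusion.** The point holds for the method-failure Pearl Index and the method-failure life table, and should be corrected before pregnancies are classified. Followed as written, the rule permits a discretionary exclusion, made with the outcome known, that removes failures without removing comparable non-pregnant cycles. The excluded pregnancy's own cycle also leaves the denominator, but that is one cycle among thousands and does not change the direction.

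The size is a fall of 10% to 25% per exclusion. It rests on an assumed 4 to 10 method failures and on at least one exclusion actually being made; the documents give no event counts. The 4 of 13 figure takes the preceding cycle to mean the one immediately before conception. The primary Pearl Index on evaluable cycles and the overall Pearl Index do not use this definition and are unaffected. A reader might give the endpoint key status, but the SAP lists it as one secondary endpoint among several.

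**What to change.** In SAP 2.2.2 and 5.5, remove the DRSP clause from the main method-failure classification. Judge intake from returned medication and the e-diary, which are planned for the whole treatment period, and keep the other listed criteria.

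Report DRSP-based exclusions only as a sensitivity analysis that shows the index with and without them. For that analysis, state the qualifying sample, the decision-maker, and a concentration limit by time after dose. Fix the limit without knowledge of pregnancy, and apply it alike to every pregnant and non-pregnant cycle that a sample can inform.

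The cost is an edit in two SAP sections and one added output. If the full protocol carries the same clause, the change must also be recorded as a departure from it; this cannot be checked from the synopsis. The downside is that a pregnancy in a woman with a falsified diary stays counted in the main index, which may then be slightly less favourable.

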2.2 Trial Endpoints

2.2.1 Primary Efficacy Endpoints

The primary efficacy endpoint will be the Pearl Index (PI) based on evaluable cycles in non-breastfeeding women aged ≤ 35 years (at the time of trial enrolment).

PI = number of pregnancies*1300/number of evaluable medication cycles

An evaluable cycle is a cycle with intercourse without back-up contraceptive at least once per month based on the electronic diary question 'Did you have sexual intercourse since the beginning of the cycle?' and will be included in the primary analysis. If the cycle is not evaluable but the subject became pregnant in this cycle, the cycle has to be included in the analysis.

Pregnancies following premature termination of IMP will be excluded from the calculations if the estimated date of conception occurs later than seven days after the last tablet intake (active or placebo).

Date of conception will be determined by using the following information:

1. Ultrasound (the date of conception must be based on the most accurate method i.e. the first trimester ultrasound. Subsequent ultrasounds will not be allowed to change dating based on this initial assessment).
2. Ultrasound (in case the first trimester ultrasound was not performed)
3. Quantitative β -hCG
4. Qualitative urine β -hCG determination
5. Estimation of gestational age based on pelvic and/or abdominal examination or pregnancy outcome
6. Investigator's estimation in the absence of the above criteria

Medication cycle will be defined as 28 days starting with the administration of the first tablet from the blister containing 28 tablets and ending with the last day of intake.

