3. ANALYSIS SETS AND SUBGROUPS

3.1 Analysis Sets

As described in the “CF111303: Site 104: Addendum to Investigation Report Signed 18-August-2016 by [name], SCOPE CRA Manager”, “CF111303: Site 120: Addendum to Serious Breach Reporting Form Signed 23-August-2016 by [name], SCOPE Project Manager” and sponsor letter “RE: Clinical Trial CF111-303: exclude data from analysis for sites 104 and site 120” data from sites 104 and 120 will not be included in any statistical summary or analysis tables. Data from these sites will only be included in the Appendix 4 tables (Tables 15.1.1.1.1, 15.1.2.1.1, 15.1.3.1.1, 15.2.1.2.5, 15.2.1.2.7, 15.2.1.4.3, 15.2.1.4.5, 15.2.1.4.7, 15.2.1.4.9, 15.2.3.1.1 and 15.2.3.1.2), Appendix 5 listings and Appendix 6 figures (Figures 15.1.1.1, 15.1.2.1).

The analyses will be based on the following analysis sets:

Enrolled Set (ES) will consist of all subjects who signed informed consent/assent.

Safety Set (SS) will consist of all subjects who:

- took at least one dose of IMP.

Full Analysis Set (FAS) will consist of all subjects who:

- took at least one dose of IMP;
- were not pregnant at the date of first IMP intake.

Modified Full Analysis Set (MFAS) will consist of all subjects who:

- took at least one dose of IMP;
- were not pregnant at the date of first IMP intake;
- were non-breastfeeding.

Per Protocol Set (PPS) will not be defined since PI will be calculated using three methods therefore protocol violations will be taken into account.

Data of centers 104 and 120 will be excluded for SS and FAS calculations. Data of these centers will also be excluded for MFAS calculations unless it will be specified in the header of the respective tables that data of these centers are included.

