4.6 Trial Periods

Date of the first IMP intake

The date of the first IMP intake will be defined as the date of the first IMP intake recorded in the treatment diary.

If such date is not available and subject did not return all IMP pills, Visit 1b date will be taken into account.

Date of the last IMP intake

The date of last IMP intake will be defined as the date of the last IMP intake provided in the eCRF “Trial Termination” section.

If such date is incomplete the following will be imputed:

- The date of the last day of the month, if month and year is available but the day is missing.

If such date is not available or only year is provided, last date of IMP administration recorded in subject's diary will be taken into account. If last date of IMP administration recorded in subject's diary is not available and subject did not return all IMP pills, the subject's last visit date will be taken into account.

Treatment period

The treatment period is defined as the period from the first IMP intake up to the last IMP intake.

Baseline value

Baseline value for a variable will be defined as Visit 1a value.

Absolute change

Absolute change from Visit 1a to each visit will be calculated as

$$\text{Absolute change from Baseline at Visit } <X> = \text{Value at Visit } <X> - \text{Baseline Value.}$$

Treatment cycle

Treatment cycles will be defined as 28 days periods starting on the day of the first IMP intake from the blister containing 28 tablets. No more than 13 completed cycles will be used for analysis.

Reference period

The treatment period will be grouped into reference periods as:

- Cycles 2-4
- Cycles 5-7
- Cycles 8-10
- Cycles 11-13

Overall period

- Cycles 2-13

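### Cycles begun after conception still meet the exposure and evaluable definitions, so they can add risk-free cycles to the primary and overall Pearl Index denominators; the effect is small but goes one way.

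*SAP*

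**What the plan says.** The primary endpoint in SAP section 2.2.1 is "PI = number of pregnancies*1300/number of evaluable medication cycles", in non-breastfeeding women aged 35 or under. The definitions table in section 5.5 fixes the denominator:

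- Exposure cycles are "28-day cycles, where at least one treatment diary entry of IMP intake is available". One pregnancy rule follows: "a cycle will be an exposure cycle if the subject become pregnant during this cycle regardless this cycle was a 28-day cycle or not".
- For evaluable cycles the entry reads "Cycles are exposure cycles with intercourse without back-up contraceptive at least once per cycle". The conception cycle is also kept in, whatever the intercourse answer.
- The non-evaluable list opens "Cycle will not be defined as evaluable if subject did not become pregnant and". It then gives three reasons: back-up contraception was used, there was no intercourse, or the answer is missing. Being pregnant already is not among them.

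Elsewhere, section 4.6 sets one cap ("No more than 13 completed cycles will be used for analysis"). Section 3.1 restricts the modified full analysis set to women who "were not pregnant at the date of first IMP intake", which deals with pregnancy at entry only. On detection, footnote 8 to the visit schedule says that "each subject will perform a urine dipstick pregnancy test at home at the beginning of each new medication cycle".

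**The concern.** Once a woman has conceived she is no longer at risk, so any later cycle can add to the denominator but never to the numerator. Under the section 5.5 wording, such a cycle qualifies if it is a 28-day cycle with one intake entry and one report of intercourse without back-up.

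There are two plausible routes to such a cycle:

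- Conception falls late in one cycle, and the home test at the start of the next is negative or not done. That an early test can be negative is an assumption; the documents do not discuss test sensitivity.
- Ultrasound, ranked first for dating in section 2.2.1, places conception in an earlier cycle than the one in which the test turned positive.

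At stake is the point estimate and confidence interval of the primary endpoint, the overall Pearl Index, and to a lesser degree the 5000-cycle target. All the error runs towards a more favourable result.

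**Working it through.** **Inputs.** The multiplier of 1300 comes from SAP section 2.2.1. The figures of 5000 evaluable cycles, 920 subjects, 24.8% with back-up or no intercourse, and 45% dropout come from SAP section 2.6 and the protocol synopsis. The 13 cycles per completer come from the synopsis. The number of pregnancies, *x*, and the post-conception evaluable cycles per pregnancy, *k*, are not in the documents. I assume *x* = 15 (range 5 to 25) and *k* = 0 to 1 as the main case, with 2 and 3 as extremes.

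**Step 1: the plan's own figure.** 920 × 13 × (1 − 0.248) × (1 − 0.45) = 4947 cycles, 1.1% below 5000. In reverse, 5000 / (13 × 0.752 × 0.55) = 929.9, so 930 subjects against 920. The planned size reproduces if dropouts are taken to contribute no cycles, and 5000 is a fair denominator for sizing the effect.

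**Step 2: does any rule stop the count at conception?**

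| SAP section | What it limits | Ends the count at conception? |
|---|---|---|
| 2.2.1, seven-day rule | which pregnancies count | no |
| 3.1, analysis sets | pregnancy at first intake | no |
| 4.6, trial periods | 13 completed cycles | no |
| 5.5, exposure | length and one intake entry; adds the conception cycle | no |
| 5.5, evaluable | intercourse answer; keeps the conception cycle | no |
| 5.5.1, primary analysis | applies the above in the modified full analysis set | no |

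**Step 3: effect on the primary index.** As written, PI = 1300*x* / 5000. After correction, PI = 1300*x* / (5000 − *kx*). The ratio of corrected to written is 5000 / (5000 − *kx*), and it applies equally to both confidence limits. For *x* = 15:

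| *k* | Denominator | PI | Exact Poisson 95% CI | Change |
|---|---|---|---|---|
| 0 | 5000 | 3.900 | 2.183–6.432 | none |
| 0.5 | 4992.5 | 3.906 | 2.186–6.442 | +0.15% |
| 1 | 4985 | 3.912 | 2.189–6.452 | +0.30% |
| 2 | 4970 | 3.924 | 2.196–6.471 | +0.60% |
| 3 | 4955 | 3.935 | 2.203–6.491 | +0.91% |

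The upper limits use the usual exact form (0.975 quantile, 2(*x* + 1) degrees of freedom). The upper-limit formula printed in section 5.5 gives 2.280 for *x* = 15, which is below the estimate; that is a separate matter.

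**Step 4: range.** At *k* = 1, 10 pregnancies move the index from 2.600 to 2.605 (+0.20%) and 20 move it from 5.200 to 5.221 (+0.40%). Over 5 to 25 pregnancies and *k* from 0.5 to 3, the rise is 0.05% to 1.5%. A 1% rise needs 5000 × (1 − 1/1.01) = 49.5 such cycles; a 5% rise needs 238. For the target, 15 pregnancies at *k* = 1 supply 15 cycles, or 15/5000 = 0.3%.

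**The case against.** The strongest reply is that few such cycles can occur. There is a home test every cycle with serum confirmation if it is equivocal or positive, a urine test at each visit from V1b, a monthly call, and pregnancy among the listed withdrawal reasons (SAP section 5.1.1). A woman who stops after a positive test may leave a cycle shorter than 28 days, and section 5.5 waives that length only for the conception cycle. Two such cycles would need two consecutive missed or negative tests. This stands as to size, and it is why 0 to 1 per pregnancy is the main case. It does not close the gap: testing and withdrawal act on detection and do not remove a blister already completed.

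The data review could also catch these cycles. Section 3.3 assigns each pregnancy to a category and cycle, using listings of pregnancies and of treatment cycles, and Table 15.1.7.1.2 reports excluded cycles. However, no rule is given for cycles after the assigned one, and deviations are graded by their impact on perfect cycles, not on exposure or evaluable cycles.

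A reader might infer four stronger things, which the documents do not support:

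- *Every pregnancy brings one or two such cycles.* Nothing in the documents establishes this, and the testing schedule argues against it.
- *The method-failure index is lowered in the same way.* Perfect cycles exclude those affected by a protocol deviation. The exclusion-criteria table in section 3.3 gives pregnancy an impact on all cycles and cites the listing of women who became pregnant during the study. That mapping is unclear, but it may give partial protection.
- *The life table proves the intended cut-off.* Section 5.5.2 runs time to the pregnancy without saying whether that means conception or detection. The contrast is suggestive only.
- *The trial's conclusion is at risk.* The supplied text states no Pearl Index or confidence-limit threshold. The shift at *k* = 1 is 0.012 against an interval width of 6.432 − 2.183 = 4.249, about 0.3% of it.

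The protocol supplied is the synopsis, so any fuller discontinuation rule in its body, which would bear on how often such cycles arise, cannot be weighed.

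**Conclusion.** The gap is real and minor. As worded, the exposure and evaluable definitions admit cycles that start after conception, and no other section examined removes them from the primary or overall Pearl Index. The direction is certain, because these cycles add no event and so can only lower the index and both its limits. The size is uncertain and small: about 0 to 0.3% of the primary index with 15 pregnancies in 5000 cycles and 0 to 1 such cycle each, and 0.6% at 2 each. Both the pregnancy count and the cycles per pregnancy are assumptions. The method-failure index may be partly protected. No pass or fail decision is shown to turn on this point. It deserves correction because it touches the primary denominator, the error is one-sided and the remedy is cheap.

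**What to change.** Add to the exposure-cycle definition in SAP section 5.5:

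> For a woman with an on-drug pregnancy counted in the given analysis (confirmed only, or confirmed plus suspected non-confirmed), the cycle of conception is the last exposure cycle; later cycles are not exposure, evaluable or perfect cycles.

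Tying the cut-off to the pregnancies counted in each table matters because the primary table uses confirmed pregnancies only, while several added tables also include suspected, non-confirmed ones. The numerator and denominator then follow the same convention in each.

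No new data are needed: the estimated conception date is taken from the pregnancy notification form, and the data review already assigns the cycle. The cost is one sentence, a small programming change, and an index that is very slightly less favourable.
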